### **8.2 Hypotheses**

The null hypothesis ( $H_0$ ) is that the mean reduction in cylindrical power of the eye for the toric group ( $\mu_T$ ) is less than or equal to the mean for the sphere control group ( $\mu_C$ ). The alternative hypothesis ( $H_1$ ) is that the mean reduction in cylindrical power of the eye for the toric IOL group is greater than the mean for the control group.

$$\begin{aligned}H_0: \mu_T &\leq \mu_C \\H_1: \mu_T &> \mu_C\end{aligned}$$

### 8.3 Statistical Methods

Continuous variables will be summarized by treatment using the sample size, mean, standard deviation, minimum, and maximum. Categorical variables will be summarized by treatment using frequencies and percentages. Missing data will not be imputed.

The preoperative keratometric cylinder (D) will be calculated as the difference between the preoperative steep and flat keratometric powers (both in diopters). The postoperative manifest refraction cylinder (PMRC) will be referenced to the corneal plane assuming a vertex distance of 13 mm as follows.

$$PMRC = \left| \frac{1000(Sph + Cyl)}{1000 - 13(Sph + Cyl)} - \frac{1000 Sph}{1000 - 13 Sph} \right|$$

Where:

- PMRC = the postoperative manifest refractive cylinder at the corneal plane (D)
- Sph = the postoperative manifest refraction sphere at the spectacle plane (D)
- Cyl = the postoperative manifest refraction cylinder at the spectacle plane (D)

Reduction in the cylindrical power of the eye (D) will be computed as the preoperative keratometric cylinder minus the PMRC and summarized using continuous summary statistics by treatment. The statistical hypotheses will be tested using a two-sample t-test assuming unequal variances. If the one-sided p-value is less than 0.025 (or, equivalently, the two-sided p-value is less than 0.05 and the treatment difference is greater than zero), then the null hypothesis will be rejected and the toric IOL will be statistically successful in this outcome. A two-sided 95% confidence interval around the treatment difference will be reported.

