#### **6 Study Design and Methods**

##### **6.1 General Study Design**

The performance of the enVista Toric IOL will be compared with that of the enVista non-Toric (spherical) IOL. At least 384 eyes (n= 192 per lens type) from 3-4 Canadian centers will be investigated.

This is a retrospective chart review for preoperative and postoperative data conducted at least 4 weeks after IOL implantation.

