#### **6.2 Study Population**

##### **6.2.1 Inclusion Criteria**

- Males and Females subjects age 18 or older on the date of the surgery
- Implant of enVista 0.9D Toric IOL or enVista non-Toric (spherical) IOL in at least one eye
- Data available at least 4 weeks after IOL implantation
- Eyes must qualify for the 0.9D toric lens based on the Barrett Toric Calculator (flipped axis must be less than 0.2D) (<https://ascrs.org/tools/barrett-toric-calculator>)
  - Study eyes were implanted with the 0.9D toric lens
  - Control eyes were not implanted with the 0.9D toric lens and implanted with a spherical (non-toric) equivalent instead

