## **7 Study Procedures**

### **7.1 Date Range of the study**

Cases will be included in the study if they received an initial enVista IOL on or after 01-Sep-2018.

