### **7.4 Variable Abstraction**

The following clinical endpoints to be collected from subject's medical records:

- Subject Demographics and Medical History
  - Include lens calculation data: IOL power selected, predicted residual spherical equivalent refraction, surgically induced astigmatism (SIA), incision angle.
  - If toric IOL: Also include predicted residual cylinder and axis, target axis of placement, and actual axis of placement
- Keratometry (K steep/K flat with axis): Preoperative and Postoperative
- Manifest Refraction (sphere/cylinder/axis): Preoperative and Postoperative
- UCDVA: Preoperative and Postoperative
- BCDVA: Preoperative and Postoperative
- IOL Rotation: If available, also include actual vs. target (Toric IOLs only)
- The presence of any device related adverse events.

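### Device-related events are abstracted only as present or absent, without onset or follow-up time, so the crude percentages by lens depend on chart length and may mislead if follow-up differs between lenses

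*Combined protocol and SAP*

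**What the plan says.** The safety content of the plan is one line in section 7.4: "The presence of any device related adverse events". That section lists no event type, onset time or count, and no length of chart observation.

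Section 8.3 has no rule written for adverse events. The rule that fits a present/absent variable is general: "Categorical variables will be summarized by treatment using frequencies and percentages".

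Follow-up has a lower bound only. Section 6.2.1 requires "Data available at least 4 weeks after IOL implantation", and section 6.1 describes a "retrospective chart review for preoperative and postoperative data conducted at least 4 weeks after IOL implantation". Section 7.1 gives a start date and no end: "Cases will be included in the study if they received an initial enVista IOL on or after 01-Sep-2018". No data cut-off, common event window, exposure denominator or follow-up summary by lens appears anywhere.

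The only hypothesis (section 8.2), test and confidence interval (section 8.3) and power statement (section 8.4) concern the reduction in cylinder.

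**The concern.** A cumulative percentage of eyes with an event has meaning only with its observation period. Under the plan as written, an eye with a 4-week chart and no event counts the same as an eye with a much longer chart and no event. This affects the figure for each lens on its own, because a reader could not tell whether it means by week 4 or over some longer time.

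It also affects the two figures when they are set side by side. The study is a non-randomised chart review, so nothing in the design makes follow-up equal between lenses. If one lens has longer charts and events continue to arise after the early weeks, that lens will show the higher percentage at the same true risk. The listed fields would not let the sponsor detect this or correct for it. What is at stake is the reading of a descriptive safety table, not the primary result.

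**Working it through.** **The plan's own figure.** The documents give no event rate and no follow-up figure to reproduce. The one computed figure is the sample size in section 8.4. With a difference of 0.25 D, SD 0.753 D and one-sided 2.5%, a noncentral t calculation at 192 eyes per group gives power 0.9006, and 192 is the smallest number reaching 90%. It reproduces, but it concerns cylinder reduction and does not bear on this point. Only the 192 eyes per lens is carried forward.

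**Inputs**
- Eyes per lens: 192 (sections 6.1 and 8.4).
- Minimum follow-up: 4 weeks (sections 6.1 and 6.2.1). Maximum: not stated.
- Event rate: assumed, constant over time and equal in both lenses, at 1, 2 or 5 per 100 eye-years.
- Mean follow-up: assumed, at 13 weeks, 26 weeks or 1 year (52.18 weeks).

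**Formula.** Expected crude percentage = 1 − exp(−rate × follow-up in years). It treats every eye in a group as followed for the group mean. At rates this low the percentage is nearly linear in time, so the mean is an adequate summary.

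**Example at 2 per 100 eye-years**
- 26 weeks: 1 − exp(−0.02 × 26/52.18) = 0.99%; × 192 = 1.9 eyes.
- 1 year: 1 − exp(−0.02) = 1.98%; × 192 = 3.8 eyes.
- Ratio 2.0, with no true difference.

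**Range**

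| Rate per 100 eye-years | 26 weeks each | 26 weeks vs 1 year | 13 weeks vs 1 year |
|---|---|---|---|
| 1 | 0.50% vs 0.50%, ratio 1.0 | 0.50% vs 1.00%, ratio 2.0 | 0.25% vs 1.00%, ratio 4.0 |
| 2 | 0.99% vs 0.99%, ratio 1.0 | 0.99% vs 1.98%, ratio 2.0 | 0.50% vs 1.98%, ratio 4.0 |
| 5 | 2.46% vs 2.46%, ratio 1.0 | 2.46% vs 4.88%, ratio 2.0 | 1.24% vs 4.88%, ratio 3.9 |

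The ratio follows the ratio of mean follow-up and hardly depends on the assumed rate. In eyes, the 26-week against 1-year gap is about 1 at the lowest rate (0.95 vs 1.91) and about 5 at the highest (4.72 vs 9.36).

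**Does eye-time remove it?** At 2 per 100 eye-years, 26 weeks gives 192 × 26/52.18 = 95.7 eye-years and 1.90/95.7 = 1.99 per 100. One year gives 192 eye-years and 3.80/192 = 1.98 per 100. The gap disappears.

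**If all events fall before week 4.** Longer charts then add no events, and the crude percentages are not distorted by chart length. The eye-time rate would be: the same count divided by 95.7 and by 192 eye-years differs by a factor of 2.0. That is why a fixed early window is needed as well as the eye-time rate. The window alone would be sparse under a constant rate: by week 4 the expected percentage is 0.08% to 0.38%, or 0.15 to 0.73 of 192 eyes, for rates of 1 to 5 per 100 eye-years.

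**The case against.** The strongest reply is that the plan contains no safety endpoint and no safety hypothesis, and that the sentence on categorical variables is generic and does not mention events. That is correct. The point therefore concerns a descriptive item, and it would be wrong to say that a planned comparison fails. The sentence still governs, because no other rule in section 8.3 could apply to a present/absent variable.

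A second reply is that both lenses come from the same small set of centres ("At least 384 eyes (n= 192 per lens type) from 3-4 Canadian centers will be investigated"), under one start date and one minimum. This makes similar follow-up plausible. It does not establish it, since the documents do not say that each centre supplies both lenses or that both were used over the same period.

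A third is that section 7.4 is a list of endpoints, not an eCRF specification. Surgery dates must be known for eligibility, and section 9.3 keeps the subject linkage until cleaning and analysis are done. So sites could go back to the charts during analysis. That stands, but after the linkage is destroyed they could not.

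A reader might infer three stronger things, and the documents support none of them.
- That follow-up runs from 4 weeks to years. Only the floor is stated; the upper end is an inference from the open window.
- That event percentages cannot be compared between lenses. Distortion needs both unequal follow-up and events arising after the early period, and the documents show neither.
- That the distortion could be about 26-fold. That follows from 0.15% at 4 weeks against 3.92% at 2 years at 2 per 100 eye-years. The arithmetic is right, but it puts every eye of one lens at the minimum and every eye of the other at 2 years, and nothing in the documents suggests that contrast.

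Finally, section 6.2.2 excludes eyes on postoperative BCDVA and, for toric eyes only, on rotation. This selection on outcome limits any safety comparison however follow-up is handled.

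**Conclusion.** The point holds as a minor one. Events are abstracted as presence only, follow-up has a floor and no stated ceiling, and the only applicable summary is a crude percentage, so each lens's figure depends on chart length that is not among the listed variables. Whether the figures mislead between lenses depends on whether follow-up differs, which the documents do not show.

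The size rests on an assumed constant rate, equal in both lenses. The crude percentages then differ roughly in proportion to mean follow-up: about 2-fold or 4-fold in the unequal cases above, and not at all when follow-up is equal. At 2 per 100 eye-years the 2-fold case is a gap of about two eyes in 192 per lens. The primary test, its sample size and its conclusion are unaffected.

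**What to change.** In section 7.4, add for each eye the days from surgery to the last eye examination in the chart and, for each device-related event, its type and the days from surgery to onset. Elapsed days serve the purpose without entering dates, which suits the bar on identifiers in the eCRF in section 9.1.

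In section 8.3, replace the crude percentage as the sole summary with:
- the number and percentage of eyes with an event by lens from surgery to week 4, a window that section 6.2.1 requires every included eye to complete;
- events by lens over all follow-up, per eye-time at risk;
- the distribution of follow-up by lens.

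State beside the table that the postoperative exclusions in section 6.2.2 still limit any safety comparison between lenses; neither summary removes them.

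The cost is two or three eCRF fields, one extra table and slightly longer abstraction per chart. The fields should be in place before abstraction starts, and at the latest before the linkage is destroyed under section 9.3.

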##### **6.1.1 Total Number of Subjects**

The study will enroll at least 384 eyes presenting with at least 192 enVista Toric 0.9D IOLs and 192 enVista non-Toric (spherical) IOLs.

It is expected that the medical records of approximately 600 subjects will need to be evaluated in order to identify the required 384 eyes that are eligible for inclusion in this study.

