### **6.2.2 Exclusion Criteria**

- History of uncontrolled or clinically significant ocular comorbidities for the treated eye(s) before the surgery (e.g., dry eyes, retinal pathology, etc.)
- BCDVA of 20/25 or worse for the treated eye(s) after the surgery
- Excessive IOL rotation > 10 degrees (Toric IOLs only) for the treated eye(s) after the surgery

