### 8.4 Sample Size and Power

A sample size of 192 eyes in each group will have 90% power to detect a difference in means of 0.25 D assuming that the common standard deviation is 0.753 D using a two-group Satterthwaite t-test with a 2.5% one-sided significance level.

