## 9 Study Administration

### 9.1 Data Collection and Management

Paper source document worksheets will be created to capture all study related data. Data recorded in these worksheets will be entered into an electronic Case Report Form (Dacima eCRF) by qualified site personnel.

Access to the eCRF will be password restricted to designated and appropriately trained site personnel.

Subject identifiers will not be entered into the eCRF. Subjects will be identified by a subject number that will be sequentially assigned to each eligible medical record (i.e., subject).

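### The primary t-test, its 95% CI and the 90% power treat 384 eyes as independent, but nothing limits a subject to one eye

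*Combined protocol and SAP*

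**What the plan says.** The unit of counting is the eye. Section 6.1 states "At least 384 eyes (n= 192 per lens type) from 3-4 Canadian centers will be investigated", and section 6.1.1, although headed as a number of subjects, sets its target in eyes only: "The study will enroll at least 384 eyes presenting with at least 192 enVista Toric 0.9D IOLs and 192 enVista non-Toric (spherical) IOLs". It adds a screening forecast: "It is expected that the medical records of approximately 600 subjects will need to be evaluated in order to identify the required 384 eyes". The number of subjects who will supply those eyes is not given.

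Eligibility leaves room for two eyes per subject. Section 6.2.1 requires "Implant of enVista 0.9D Toric IOL or enVista non-Toric (spherical) IOL in at least one eye", and the exclusions in section 6.2.2 are worded for one or more treated eyes, for example "BCDVA of 20/25 or worse for the treated eye(s) after the surgery". No section limits a subject to one eye, says which eye to take, or says how two eligible eyes of one subject are analysed.

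For the primary endpoint, section 8.3 says "The statistical hypotheses will be tested using a two-sample t-test assuming unequal variances". Success is declared at one-sided p below 0.025, and a two-sided 95% CI is reported. Section 8.4 says "A sample size of 192 eyes in each group will have 90% power to detect a difference in means of 0.25 D", assuming a common SD of 0.753 D and a Satterthwaite t-test at one-sided 2.5%. Neither section has a term for subject or a design effect.

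**The concern.** The unequal-variance (Satterthwaite) form of the t-test allows for different variances in the two lens groups. It does not allow for correlation between two eyes of one person. Preoperative corneal cylinder and postoperative refraction can be correlated between fellow eyes, so two eyes of one subject may carry less, or differently structured, information than two eyes of two subjects.

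The estimated difference in means is not the issue; its standard error is. With positive between-eye correlation, same-lens pairs make the test anti-conservative and the interval too narrow, while split pairs make the test conservative and the interval too wide. Charts are selected at each site and nothing controls the mix. A reader of the result could not tell whether the 0.025 threshold, the 95% interval and the 90% power apply.

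**Working it through.** **Inputs from the documents.** 192 eyes per group, difference 0.25 D, SD 0.753 D, one-sided alpha 0.025 (sections 8.3 and 8.4).

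**Assumed inputs.** b, the share of eyes whose fellow eye is also in the study, and rho, the between-eye correlation of the outcome. The documents give neither, so a range is shown.

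**Step 1: the plan's own figure.** The noncentrality is 0.25 / (0.753 × √(2/192)) = 3.253. Noncentral-t power with 382 df is 90.06%. At 191 per group it is 89.91%. The stated 90% therefore reproduces for independent eyes, and 192 is the smallest group size that reaches it.

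**Step 2: variance with paired eyes.** For independent eyes the variance of the difference in means is 2σ²/n.
- Same-lens pairs: each group has nb/2 pairs, each adding 2·rho·σ² to the variance of the group sum. The variance of the difference becomes (2σ²/n)(1 + b·rho).
- Split pairs: there are nb pairs across the two groups, so the covariance of the two means is b·rho·σ²/n. The variance becomes (2σ²/n)(1 − b·rho).

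Call the factor D. The planned test uses D = 1 whatever the pairing.

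**Step 3: consequences.**
- True one-sided alpha = 1 − Φ(1.96/√D); coverage = 1 − 2 × alpha.
- Rejection rate of the planned test at 0.25 D = 1 − Φ((1.96 − 3.253)/√D).
- Power of a correctly sized test = noncentral-t power at 192/D eyes per group.
- Eyes per group to hold 90% = 192 × D.

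| Pairing | b | rho | D | Alpha | Coverage | Planned test rejects | Correctly sized power | Eyes per group for 90% |
|---|---|---|---|---|---|---|---|---|
| None | 0 | – | 1 | 0.025 | 95% | 90% | 90% | 192 |
| Same lens | 0.25 | 0.3 | 1.075 | 0.0294 | 94.1% | 89.4% | 87.9% | 207 |
| Same lens | 0.5 | 0.5 | 1.25 | 0.0398 | 92.0% | 87.6% | 82.7% | 240 |
| Same lens (upper bound on b) | 1 | 0.5 | 1.5 | 0.0548 | 89.0% | 85.5% | 75.4% | 288 |
| Split | 0.5 | 0.5 | 0.75 | 0.0118 | 97.6% | 93.2% | 96.3% | – |

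With 25% of eyes in same-lens pairs and 25% in split pairs at rho = 0.5, D = 1 + 0.125 − 0.125 = 1, and the effects cancel.

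**Step 4: simulation.** In 20,000 null trials per scenario, the planned test and a test with subject-clustered standard errors rejected as follows:

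| Scenario | Planned test | Clustered |
|---|---|---|
| Same lens, b = 0.25, rho = 0.3 | 0.029 | 0.025 |
| Same lens, b = 0.5, rho = 0.5 | 0.040 | 0.025 |
| Same lens, b = 1, rho = 0.5 | 0.055 | 0.026 |
| Split, b = 0.5, rho = 0.5 | 0.011 | 0.023 |
| Equal mix, rho = 0.5 | 0.024 | 0.025 |

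Clustered coverage was 94.8% to 95.2%. With unequal SDs (0.6 and 0.9, assumed), b = 0.5 and rho = 0.5, the planned and clustered rates were 0.039 and 0.024 for same-lens pairs, and 0.013 and 0.026 for split pairs.

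**The case against.** The strongest reply is that the problem is conditional and the documents do not show that the condition is met. The eligibility wording permits two eyes but does not say both will be analysed, and about 600 subject records for 384 eyes is compatible with one eye each. That is right, and the magnitude cannot be settled from the documents. But a screening forecast is not a rule, and the plan as written lets both eyes in.

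Second, the range may overstate the effect. The b = 1 row needs every subject to contribute two eyes with the same lens, each passing the toric-calculator and postoperative criteria. It is a bound, not an expectation. At b = 0.1 the effect is small: alpha 0.027 and correctly sized power 89.2% at rho = 0.3, or 0.028 and 88.6% at rho = 0.5. Direction also depends on the pairing. All of this stands. It limits the size of the problem, not its existence.

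Third, the target is a floor, so there may be more eyes than 192 per group; 207 independent eyes would give 92.1%. True, but section 8.4 computes power at exactly 192, and that minimum has no margin. Extra eyes would also not repair the alpha or the coverage of the planned test.

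Fourth, a one-eye rule would keep the planned t-test valid. It would, provided 384 eligible subjects can be found. It is a legitimate alternative, and its cost is given with the fix.

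**Conclusion.** The concern holds as a conditional gap in the primary analysis and should be fixed before the data are analysed. The 90% power is not an arithmetic error; it rests on an independence assumption that the eligibility rules do not secure. If no subject contributes two eyes, or if same-lens and split pairs balance, the stated properties stand. Otherwise, over the assumed values shown, one-sided alpha runs from 0.012 (split pairs) to 0.040 (half the eyes in same-lens pairs), with 0.055 as the bound when every eye is in a same-lens pair at rho = 0.5. Coverage runs from 97.6% down to 92.0%, with about 89% at that bound. Confidence is high that the plan leaves this open; the size is unknown because b and rho are unknown.

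**What to change.** In section 8.3, replace the two-sample t-test with a linear model of eye-level reduction on lens type, with robust standard errors clustered on subject. Keep the one-sided 0.025 rule and the two-sided 95% CI. The estimate is still the difference in group means, the allowance for unequal variances is kept, same-lens and split pairs are both handled, and with no bilateral subjects the result matches the planned test. If a mixed model with a random subject effect is preferred, allow a separate residual variance for each lens group.

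In section 8.4, say that 90% power holds only for independent eyes, and restate power over an assumed range of b and rho. Report the number of subjects, same-lens pairs and split pairs.

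The cost is SAP wording and a different model call. No new data item is needed, because section 9.1 already assigns a number to each subject. The stated power may fall to about 88%, 83% or 75% in the three same-lens cases in the table. If that is accepted, no extra eyes are needed; holding 90% would take about 207, 240 or 288 eyes per group.

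The alternative is a pre-specified one-eye rule, which leaves the t-test and section 8.4 unchanged if 384 subjects are available. Applied to a fixed set of 384 eyes it costs more: with half the eyes in same-lens pairs, 192 × (1 − 0.5/2) = 144 per group remain, with 80% power.

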## **8 Statistics**

### **8.1 Primary Effectiveness Endpoint**

The primary effectiveness endpoint is the mean reduction in cylindrical power of the eye. Reduction in the cylindrical power of the eye is defined as the difference between the magnitudes of the preoperative keratometric cylinder and the residual refractive cylinder (referenced to the corneal plane).

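### The only test in this non-randomised chart review is an unadjusted Welch t-test; estimates adjusted for steep axis, site and preoperative cylinder should be prespecified beside it

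*Combined protocol and SAP*

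**What the plan says.** Section 6.1 gives the design: "This is a retrospective chart review for preoperative and postoperative data conducted at least 4 weeks after IOL implantation". It also says: "At least 384 eyes (n= 192 per lens type) from 3-4 Canadian centers will be investigated". The quota is by lens type, not by lens type within centre.

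Section 6.2.1 requires every eye to qualify for the 0.9 D toric lens on the Barrett calculator and then defines the comparator: "Control eyes were not implanted with the 0.9D toric lens and implanted with a spherical (non-toric) equivalent instead". It does not say why a qualifying eye received the spherical lens. It admits subjects on the basis of "Implant of enVista 0.9D Toric IOL or enVista non-Toric (spherical) IOL in at least one eye", so one subject may contribute two eyes.

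The endpoint in section 8.1 compares magnitudes: "Reduction in the cylindrical power of the eye is defined as the difference between the magnitudes of the preoperative keratometric cylinder". The quantity subtracted is the manifest cylinder left after surgery, taken to the corneal plane. Axis does not enter the endpoint.

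Section 8.2 sets a one-sided hypothesis about two group means. Section 8.3 says: "The statistical hypotheses will be tested using a two-sample t-test assuming unequal variances", with a 95% confidence interval for the difference. If the one-sided p-value is below 0.025, "then the null hypothesis will be rejected and the toric IOL will be statistically successful in this outcome". The rest of section 8.3 is descriptive summaries by treatment and the endpoint formula. No covariate, site term, stratification, matching or sensitivity analysis appears in sections 8.1 to 8.4.

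Section 7.4 collects keratometry with axis, surgically induced astigmatism (SIA) and incision angle for all eyes. The main candidates for adjustment are therefore already in the data set.

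**The concern.** Randomisation did not form these groups; practice did. If toric and spherical eyes differ in steep axis, or come in different proportions from centres that differ in incision, measurement or refraction practice, the difference in mean reduction mixes those factors with the lens. Section 8.3 then credits the lens.

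Preoperative cylinder is a partial case. It enters by subtraction, which may or may not be enough to deal with an imbalance.

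With no adjusted result prespecified, a reader cannot see whether a positive finding survives these factors, and any adjustment added after seeing the data would be post hoc.

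**Working it through.** **1. Inputs.** From section 8.4: 192 eyes per group, common SD 0.753 D, difference 0.25 D, one-sided 2.5%. Not in the documents, and therefore assumed below: any imbalance, any covariate effect, the reliability of keratometry and the site mix.

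**2. The plan's own figure.** SE = 0.753 × √(2/192) = 0.0769 D. With 382 degrees of freedom the critical value is 1.966, so success needs an observed difference of about 1.966 × 0.0769 = 0.151 D. Noncentral-t power at 0.25 D is 0.901 with 192 eyes per group and 0.899 with 191. The stated 192 and 90% reproduce.

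**3. From bias to false success.** With no lens effect and a bias B, the noncentrality is B/SE.

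| Bias (D) | B/SE | Chance of declaring success |
|---|---|---|
| 0 | 0 | 2.5% |
| 0.025 | 0.325 | 5.1% |
| 0.04 | 0.520 | 7.5% |
| 0.05 | 0.651 | 9.5% |
| 0.10 | 1.301 | 25.4% |

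In the other direction, a bias of −0.10 D with a true lens effect of 0.25 D cuts power from 90% to 49%.

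**4. What would produce such a bias through axis or site.** For a two-level factor, bias = difference in share × difference in mean reduction. If the two levels differ by 0.25 D in mean reduction, shares 10, 20 or 40 points apart give 0.025, 0.05 or 0.10 D. A site holding 70% of the toric eyes and 30% of the spherical eyes, with site means 0.10 D apart, gives 0.40 × 0.10 = 0.04 D. In 40,000 simulated trials of that last case (one eye per subject), Welch declared success in 7.2% and the site-adjusted model in 2.3%.

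**5. Preoperative cylinder.** Suppose residual cylinder depends on true preoperative cylinder with slope b, measured keratometric cylinder has reliability r, and the groups differ by d in mean measured cylinder. With no lens effect the bias depends on what drove lens choice:

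- Choice followed true cylinder: unadjusted (1−b)d; adjusted for measured cylinder −b(1−r)d.
- Choice followed recorded keratometry: unadjusted (1−br)d; adjusted 0.

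At d = 0.10 D, as unadjusted / adjusted bias in D:

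| b, r | Choice by true cylinder | Choice by recorded keratometry |
|---|---|---|
| 0.5, 1 | +0.05 / 0 | +0.05 / 0 |
| 1, 0.5 | 0 / −0.05 | +0.05 / 0 |
| 1, 0.8 | 0 / −0.02 | +0.02 / 0 |
| 0.8, 0.8 | +0.020 / −0.016 | +0.036 / 0 |

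So adjustment for measured cylinder can remove bias or add some, and the documents do not say which mechanism applied.

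**6. Price of a site term.** For two equal sites, with p the toric share at one site, the variance of the lens estimate is multiplied by 0.25/[p(1−p)]. That is 1.19 at 70/30 and 1.56 at 80/20. Power at 0.25 D becomes about 84% and 74%, assuming the covariates explain none of the outcome variance.

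**The case against.** The strongest reply has four parts.

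- **The hypothesis concerns two means, and Welch tests exactly that.** This stands. The gap lies between the hypothesis and crediting the lens. Section 8.3 does limit its claim to this one outcome.
- **Comparability is already addressed.** In part. The shared Barrett criterion restricts both groups to eyes suited to one cylinder power, and subtraction takes out some baseline difference. Neither balances steep axis or site.
- **By-treatment summaries are planned.** This also stands in part: most of a balance table follows from sections 7.4 and 8.3. A table shows imbalance but does not adjust for it.
- **Every bias figure is assumed.** True. No imbalance is documented, and the 0.25 D contrast used for axis or site equals the whole design effect in section 8.4.

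A reader might go further and infer that the unadjusted and cylinder-adjusted estimates must bracket the truth. The documents do not support this. It requires lens choice to have followed true cylinder, whereas if choice followed recorded keratometry the adjusted estimate is unbiased and the unadjusted one is not.

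A reader might also infer that success should require significance in Welch and in both adjusted models. That is a trade-off, not a necessity. In simulated scenarios with lens use following site, or with keratometry error, it reduced power at 0.25 D to between 71% and 84%.

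**Conclusion.** The point holds as a gap in the plan that should be closed, with medium confidence. In a non-randomised comparison, the sole inferential analysis ignores steep axis and site and handles preoperative cylinder only by subtraction, although axis and keratometry are collected.

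The size is illustrative: 5.1%, 9.5% or 25.4% false success at a bias of 0.025, 0.05 or 0.10 D, on the SD and sample size in section 8.4. The direction is unknown.

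A reader might infer that the Welch test is invalid, that the study is underpowered, or that its error rate is in fact inflated. The documents support none of these. The test fits its hypothesis, the power reproduces, and no imbalance is reported.

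**What to change.** In section 8.3:

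1. Keep the Welch test for the null hypothesis.
2. Prespecify linear models of cylinder reduction on lens group, steep-axis class (limits fixed in advance) and site, first without and then with preoperative keratometric cylinder. Cluster standard errors by subject, since both eyes may enter.
3. Report these lens estimates with 95% confidence intervals beside the Welch result.
4. Tabulate preoperative cylinder, steep axis, SIA, incision angle and site by lens group.
5. State that success will be described as a lens effect only to the extent that the adjusted estimates support it, and that any disagreement will be reported as dependent on baseline adjustment.

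The cost is SAP wording, site as an analysis variable and one table. Keratometry with axis, SIA, incision angle (section 7.4) and a subject number (section 9.1) are already collected. No joint p-value rule and no added eyes are required.

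The downside is a wider adjusted interval if lens use follows site, as in step 6 of the working. If site nearly determines the lens, no model can separate them. Adjustment also reaches recorded baseline factors only. It does not correct for unrecorded reasons for lens choice or for the exclusions in section 6.2.2 that rest on postoperative findings.
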